3.9 Changes from protocol-defined analyses

The following change from the protocol have been implemented in the SAP:

- The protocol stated the secondary outcome variable of 'adverse events from time of informed consent through Safety Follow-up', this will now be 'Treatment-emergent adverse events from time of informed consent through Safety Follow-up'.
- The protocol defines 'baseline' for plasma concentration data as the predose measurement 12 weeks (± 1 week) postpartum. In the SAP, tables and figures, the name for the reference point was changed to 'postpartum'.

- Clarification was added to the Enrolled Set definition to include participants who re-enrolled. The SS definition was updated to include all participants with ongoing CZP dosing at screening. PK-PPS definition was clarified to include participants for whom at least one predose or postdose sample is available which was not impacted by an important protocol deviation.

4 STATISTICAL/ANALYTICAL ISSUES

4.1 Adjustments for covariates

The following covariates will be included in the primary analysis model specified in Section 9.1.2:

- disease phenotype
- gestational week
- trimester and
- dose point

The covariates will be defined as: disease phenotype (rheumatoid arthritis, psoriatic arthritis, psoriasis, Crohn's disease, axial spondyloarthritis and ankylosing spondylitis) a 6-category variable, gestational week (that is, at the time point when sample is collected) as a continuous variable, trimester (trimester 1, 2, 3, or postpartum) as a 4-category variable, and dose point (predose or postdose) as a binary variable. In case of overfitting, disease phenotype will be excluded from the model.

4.2 Handling of dropouts or missing data

There will be no special procedures for handling missing outcome data. Only the imputation of missing or partial dates for safety assessments, as well as handling values below the LLOQ in the PK data will be conducted.

4.2.1 Handling of missing data for AE

All AEs will be considered TEAEs in this study. For analyses of TEAEs, a complete date must be established to correctly identify the TEAE as occurring during the pregnancy period or not. For purposes of imputing missing components of partially reported start and stop dates for TEAEs, the algorithms listed below will be followed.

Although the algorithms for pregnancy period or not depend on the onset date, imputation rules are provided for stop date as well, as these may be needed for certain statistical analyses, such as an analysis of TEAE prevalence or TEAE duration.

Start and stop dates of TEAEs will be displayed as reported in the study participant data listings (i.e., no imputed values will be displayed in data listings).

Imputation of Partial Start Dates

- If only the month and year are specified and the month and year of study enrolment is not the same as the month and year of TEAE onset, then use the 1st of the month
- If only the month and year are specified and the month and year of study enrolment is the same as the month and year of TEAE onset, then use the date/time of study enrolment

- If only the year is specified, and the year of study enrolment is the same as the year of TEAE onset, then use the date/time of study enrolment
- If the TEAE onset date is completely unknown, then use the date of study enrolment

Imputation of Partial Stop Dates:

- If only the month and year are specified, then use the last day of the month
- If only the year is specified, then use December 31st of that year
- If the imputed stop date is after last contact date, use last contact date.
- If the TEAE is resolved and the stop date is completely unknown, then do not impute the stop date

Other imputation

In addition, the following will apply for presenting TEAE in summary tables:

- if the intensity of an TEAE is unknown, it will be considered as severe.
- If the relationship to CZP is missing, it will be considered as related.

For seriousness, no imputation rule will be applied, the worst-case approach will be applied for the analysis of Serious TEAEs (i.e., the missing seriousness will be considered as serious if missing).

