4.2.2 Handling of missing data for prior and concomitant medications

Any medications with incomplete start and end dates/times will be handled according to the following rules for classification as prior and concomitant and for the calculation of relative study days. In the event of ambiguity or incomplete data which makes it impossible to determine whether a medication was concomitant or not, the medication will be considered as concomitant. Such imputations will only be performed for these classifications and calculations; in the listings all data will be shown as recorded on the electronic case report form (eCRF).

Imputation of Partial Start Dates

- If only the month and year are specified and the month and year of study enrolment is not the same as the month and year of the start date, then use the 1st of the month
- If only the month and year are specified and the month and year of study enrolment is the same as the month and year of the start, then use the date of study enrolment
- If only the year is specified, and the year of study enrolment is not the same as the year of the start date, then use January 1 of the year of the start date
- If only the year is specified, and the year of study enrolment is the same as the year of the start date, then use the date of study enrolment
- If the start date is completely unknown, and the stop date is unknown or not prior to the date of first dose after enrollment, then use the date of study enrollment

Imputation of Partial Stop Dates

- If only the month and year are specified, then use the last day of the month

- If only the year is specified, then use December 31 of that year
- If the imputed stop date is after last contact date, use last contact date.
- If the stop date is completely unknown, do not impute the stop date

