11.3 Adverse events

All AEs will be coded using the Medical Dictionary for Regulatory Activities (MedDRA v24.1 or later version) and characterized as treatment emergent.

The occurrence and incidence of TEAEs will be summarized by MedDRA system organ class and preferred term. The TEAEs will also be summarized by intensity and by relationship to CZP. TEAEs leading to discontinuation and serious TEAEs will also be summarized.

The following TEAE tables will be produced:

- Incidence of TEAEs Overview
- Incidence of TEAEs by SOC, HLT and PT
- Serious TEAEs
- Non-serious TEAEs
- TEAEs leading to death

- TEAEs leading to hospitalization or death
- TEAEs leading to study discontinuation
- Incidence of TEAEs by Maximum Severity
- Incidence of TEAEs by Maximum relationship
- Incidence of TEAEs by Trimester

The following TEAE of interest will be summarized in stand-alone tables:

- Serious infections including opportunistic infections (see Section 11.3.1)
- Malignancies or unspecified tumours including lymphoma
- Malignant Tumours
- Demyelinating-like disorders
- Aplastic anemia, pancytopenia, thrombocytopenia, neutropenia, and leucopenia
- Serious bleeding events

For the following AEs of interest, no additional tables will be provided, as these are included in the standard AE summaries:

- Congestive heart failure
- Lupus and lupus-like syndrome
- Serious skin reactions (e.g., Stevens Johnson Syndrome, toxic epidermal necrosis, and erythema multiforme).

Separate tables will be created to summarize each of the above TEAEs of interest by system organ class, high level term, and PT, where the TEAEs of interest are identified using standardized MedDRA queries (SMQ). An additional review cycle to confirm the targeted events will be implemented for opportunistic infections as described in Section 11.3.1.

All TEAEs and serious TEAEs will be listed using the SS. Details of serious TEAEs, TEAEs leading to death or study discontinuation will be listed. For results disclosure on public registries (e.g., ClinicalTrials.gov), TEAEs and serious TEAEs will be published.

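### The onset-date rules in SAP 4.2.1 put undated and same-year year-only adverse events in trimester 1 and can turn postpartum events into pregnancy events, so the by-trimester table is shifted early in proportion to the partial dates

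*SAP*

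**What the plan says.** SAP 4.2.1 states why onset dates are completed: "For analyses of TEAEs, a complete date must be established to correctly identify the TEAE as occurring during the pregnancy period or not". SAP 3.8 and 4.2.1 treat all adverse events as treatment-emergent. The onset rules in 4.2.1 are:

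- Completely unknown: "If the TEAE onset date is completely unknown, then use the date of study enrolment".
- Year only: if "the year of study enrolment is the same as the year of TEAE onset, then use the date/time of study enrolment". No branch covers any other year. The medication rules in SAP 4.2.2 do have one, which reads in part: "study enrolment is not the same as the year of the start date, then use January 1 of the year of the start date".
- Month and year, not the enrolment month; the rule reads in part: "study enrolment is not the same as the month and year of TEAE onset, then use the 1st of the month".
- Month and year, the enrolment month; the rule reads in part: "study enrolment is the same as the month and year of TEAE onset, then use the date/time of study enrolment".

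SAP 11.3 plans a table of "Incidence of TEAEs by Trimester". SAP 3.2.2 ends trimester 1 at 12 weeks 6 days, starts trimester 3 at 29 weeks, and starts the postpartum period the day after delivery. Protocol inclusion criterion 3 requires enrolment at 10 weeks' gestation or less. Listings show dates as reported. The SAP has no row for events whose period is unknown and no sensitivity analysis for imputed onsets.

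**The concern.** Early imputation is the cautious choice when the question is whether an event began before or after first treatment. That question does not arise here. The imputed onset decides which part of pregnancy, or the postpartum period, an event belongs to, and for that purpose early is not cautious: an event added to trimester 1 is removed from a later period.

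Safety across the course of pregnancy is a secondary objective, and the by-trimester table is the adverse event table that addresses it directly. With about 20 enrolled women, one or two misplaced events can change a row. Because imputed dates are not displayed, the table's reader cannot see how each partial date was allocated.

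**Working it through.** The documents give no figure to reproduce. Three points follow from the text alone:

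1. Enrolment (10 weeks or earlier) precedes the end of trimester 1 (12 weeks 6 days), so every onset set to enrolment falls in trimester 1.
2. The 1st of the delivery month is never after delivery, so every month-only postpartum onset in that month (where it is not also the enrolment month) is placed in pregnancy.
3. For an event after enrolment, no stated rule gives a date later than the true one. Any period error is therefore towards an earlier period.

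The size needs assumptions that are not in the documents: a constant event rate from enrolment, enrolment at *e* = 6 to 10 weeks, delivery at 40 weeks, enrolment dates spread evenly over the calendar, and follow-up ending at *E* = 40 weeks (delivery), 53 weeks (40 + 13) or 58 weeks (53 + 5, safety follow-up).

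Let T = 7(E − e) be the days of follow-up and a = 7(13 − e) the days of it in trimester 1.

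- Unknown onset, wrong period: 1 − a/T.
- An onset t days after enrolment is in the enrolment year with probability 1 − t/365. The share in a later year, with no rule, is T/730.
- Same-year year-only, wrong period: 1 − a(1 − a/730) / [T(1 − T/730)].
- Month-only, wrong period: each boundary misplaces on average (30.4 − 1)/2 = 14.7 days of onsets (30.4 = 365/12), giving 14.7 × (number of boundaries)/T.

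| | e = 6, to delivery (T = 238, a = 49) | e = 10, to safety follow-up (T = 336, a = 21) |
|---|---|---|
| Unknown, wrong | 1 − 49/238 = 79.4% | 1 − 21/336 = 93.8% |
| Year-only, no rule | 238/730 = 32.6% | 336/730 = 46.0% |
| Same-year year-only, wrong | 1 − 45.7/160.4 = 71.5% | 1 − 20.4/181.4 = 88.8% |
| Month-only, wrong | 2 × 14.7/238 = 12.4% | 3 × 14.7/336 = 13.1% |

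A simulation of 400,000 events per scenario over nine scenarios (e = 6, 8, 10 and three end points) agrees. It gives 79.5-93.8% for unknown, 72-89% for same-year year-only, 12-15% for month-only (mean shift about −14 days, maximum −30), and 29-50% of onsets in a later year.

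Effect on the table, for e = 10 and follow-up to safety follow-up. The true trimester 1 share is 21/336 = 6.25%. If a fraction f of events has unknown onset, the share becomes (1 − f) × 6.25% + f:

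- f = 2%: 8.1%
- f = 5%: 10.9%
- f = 10%: 15.6%
- f = 20%: 25.0%

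If the same fractions are month-only, it becomes 6.25% + f × 14.7/336, that is 6.3% at f = 2% and 7.1% at f = 20%.

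**The case against.** The strongest reply is that the stated purpose is binary, pregnancy or not, while most of the errors above are between trimesters. On the binary question the rules do better. With follow-up to safety follow-up, pregnancy makes up 30/48 = 62.5% (e = 10) to 34/52 = 65.4% (e = 6) of post-enrolment time, so an undated event placed at enrolment is right about two times in three. For month-only dates the binary error is about 14.7/336 = 4.4%. Counting doubtful events as occurring in pregnancy also fits the worst-case handling of missing intensity, relationship and seriousness in the same section. This stands for the binary question. It does not rescue the trimester table, where no direction is conservative.

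Several stronger readings are tempting but unsupported:

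- **That all year-only onsets go to trimester 1.** Only those in the enrolment year do. Other years have no rule, which is a gap and not an early shift.
- **That all month-only onsets go to the 1st.** In the enrolment month the enrolment date is used.
- **That every error is towards an earlier date.** Events are collected from consent, so an undated or enrolment-month event before enrolment moves later. It stays in trimester 1.
- **That the lack of a stop-date check distorts the table.** A screening event could receive an onset after its stop, but no trimester cell changes.
- **That the table is biased as a matter of fact.** That depends on how many dates are partial. Adverse events are reviewed at every visit, with predose visits every 4 weeks in pregnancy, which should keep the number of undated events down.

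**Conclusion.** The concern holds for placement of events by period. As written, the rules put unknown and same-year year-only onsets in trimester 1 whatever the truth, and put month-only postpartum onsets from the delivery month into pregnancy. For events after enrolment, every resulting error is towards an earlier period.

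Under uniform onset the error rates are about 80-94%, 72-89% and 12-15% for the three kinds of partial date. These are rates among partial dates, not among all events. The distortion of the table scales with the number of such dates. It could be material with a few per cent of unknown onsets, and is minor if only month-only dates occur.

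Overall, serious and related event incidences do not change, because all adverse events count as treatment-emergent. The PK analysis does not use these rules. The point merits correction before the by-trimester table is run, but does not threaten the study's main conclusion.

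**What to change.** For the by-trimester table, replace single-date imputation with bounds:

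- Lower bound: the later of the consent date and the earliest date consistent with the known date parts.
- Upper bound: the earliest of the known stop date, the last contact date and the latest date consistent with the known date parts.
- If the database records the visit at which each event was first reported, tighten the bounds with that visit and the preceding adverse event review. The documents schedule the reviews but do not show that this visit is recorded per event, so the fix should not depend on it.
- Assign a period only if both bounds fall in the same one. Otherwise count the event in a row for period not determinable.
- Treat year-only onsets in a year other than the enrolment year in the same way, which closes the missing branch.

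Mid-month imputation would be a partial alternative. In the simulation it cuts month-only misplacement to about 6-9%, with errors in both directions, but it does nothing for unknown or year-only onsets.

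The cost is a change to SAP wording, a small date derivation and one extra table row. Study conduct is unchanged.

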4.2.2 Handling of missing data for prior and concomitant medications

Any medications with incomplete start and end dates/times will be handled according to the following rules for classification as prior and concomitant and for the calculation of relative study days. In the event of ambiguity or incomplete data which makes it impossible to determine whether a medication was concomitant or not, the medication will be considered as concomitant. Such imputations will only be performed for these classifications and calculations; in the listings all data will be shown as recorded on the electronic case report form (eCRF).

Imputation of Partial Start Dates

- If only the month and year are specified and the month and year of study enrolment is not the same as the month and year of the start date, then use the 1st of the month
- If only the month and year are specified and the month and year of study enrolment is the same as the month and year of the start, then use the date of study enrolment
- If only the year is specified, and the year of study enrolment is not the same as the year of the start date, then use January 1 of the year of the start date
- If only the year is specified, and the year of study enrolment is the same as the year of the start date, then use the date of study enrolment
- If the start date is completely unknown, and the stop date is unknown or not prior to the date of first dose after enrollment, then use the date of study enrollment

Imputation of Partial Stop Dates

- If only the month and year are specified, then use the last day of the month

- If only the year is specified, then use December 31 of that year
- If the imputed stop date is after last contact date, use last contact date.
- If the stop date is completely unknown, do not impute the stop date

4.2.3 Handling of values below the LLOQ in PK data

Unless otherwise stated, PK measured values below the limit of quantification (BLQ) will be reported as the values of LLOQ/2 (0.016 ug/mL) for the summary statistics and figures but as BLQ for listings. No imputation will be used for missing samples.

4.3 Interim analyses and data monitoring

No interim analyses or data monitoring is planned.

4.4 Multicenter studies

No exploration of treatment by center interaction will be investigated.

4.5 Multiple comparisons/multiplicity

No adjustments for multiplicity or multiple comparisons are planned.

5 STUDY POPULATION CHARACTERISTICS

5.1 Disposition of study participants

Study participant disposition will be summarized for the ASPS. In this summary, the dates of first study participant screened and date of last study participant last visit, number of screened study participants, and the number of study participants included in each analysis set (ES, SS, PK-PPS) will be presented for all participants and by dosing regimen overall and for each site.

The disposition of study participants into dosing regimen groups and analysis sets (ES, SS and PK-PPS) will also be summarized on the ES.

Reasons for screen failures (as collected on the Study Termination Screen Failure of the case report form (CRF) page) will be summarized for the ASPS who failed to be enrolled.

The number and percentage of study participants will be summarized using the ES. The primary reason for study discontinuation as collected on the Study Termination CRF page will be provided in this table.

Finally, the number of enrolled study participants who discontinued the study due to TEAEs will be summarized.

Study disposition and termination details will be listed for the ASPS. Additional listings on the ES will be created on study discontinuation, study participant analysis sets and visit dates. A listing will also be provided for study participants who did not meet the study eligibility criteria.

5.2 Protocol deviations

A summary displaying the number and percentage of study participants with an important protocol deviation will be provided on the ES, including a summary of study participants excluded from the PK-PPS due to important protocol deviations.

A by-study participant listing of important protocol deviations will be provided for all study participants in the ES.

6 DEMOGRAPHICS AND OTHER BASELINE CHARACTERISTICS

6.1 Demographics

The following demographic variables measured at Baseline to be summarized for the ES are: age (years), country, race, height (cm), body weight (kg) and BMI (kg/m^2). Age and BMI will be summarized as continuous variables only. Gender, confirmation of pregnancy and ethnicity will only be listed.

By-study participant listings on demographics will be provided for the ASPS.

6.2 Other Baseline characteristics

Other baseline characteristics to be summarized are lifestyle characteristics based on SS.

Details of tuberculosis (TB) testing will not be summarized. TB testing will be performed if the study participant has not been tested within 6 months prior to Screening and has no associated clinical evidence of an active TB infection. However, this data is not captured in the electronic database and hence no summary table or listing will be produced.

6.3 Medical history and concomitant diseases

Previous medical history is defined as conditions that have resolved prior to study entry.

Ongoing medical history is defined as conditions that are ongoing at the time of study entry.

Previous and on-going medical history will be summarized together by MedDRA System Organ Class (SOC) and Preferred Term (PT), by dosing regimen and overall including the number and percentage of study participants with each condition. The table summaries will be ordered alphabetically for SOC and in terms of decreasing frequency for PT within SOC. In the event of ties, PT will be ordered alphabetically.

The summaries will be presented on the SS.

Medical history will be listed by dosing regimen and study participant including the reported term, PT, and SOC for the ES. A glossary of all medical history conditions will be presented including the reported term, PT and SOC.

Medical procedures and medical procedure history will be listed for all study participants on the ES.

6.4 Medical conditions leading to CZP use

Medical conditions identified as the primary condition for CZP use will be summarized using the number and percentage for the SS. Primary medical conditions for Cimzia use as well as other medical conditions reported on the electronic Case Report Form (eCRF) but not identified as primary will be included in a listing. The medical condition decodes (MHDECOD) for the listing include:

- Psoriatic arthropathy

- Psoriasis
- Rheumatoid arthritis
- Arthritis
- Ankylosing spondylitis
- Axial spondyloarthritis
- Spondylitis
- Crohn's disease
- Juvenile idiopathic arthritis

6.5 Prior and concomitant medications

Study participants are permitted to continue on their prescribed medical therapy for the disease in accordance with the instructions of their treating physician.

Any treatment other than commercial CZP (CZP dosing dates and times will be collected separately in a diary), including over-the-counter products and supplements, must be recorded in the study participant's notes (source documentation) and provided on the eCRF. This record should include the name of the drug, the dose, the route, and date(s) of administration, and the indication for use.

For the purposes of this study:

- Past medications are those that are ongoing at the time of the first day of the last menstrual period and those that started after the first day of the last menstrual period and stopped prior to entering the screening period. For participants with IVF, past medications are those that are ongoing 12 weeks prior to screening or started within 12 weeks prior to screening and stopped prior to entering the screening period.
- Prior medications are those that are ongoing at the time of the first day of the last menstrual period and those that started after the first day of the last menstrual period but prior to entering the screening period. For participants with IVF, prior medications are those that are ongoing 12 weeks prior to screening or started within 12 weeks prior to screening.
- Concomitant medications are medications with at least 1 day in common with the screening period or sampling periods.
- Prior medications may include both past medications and concomitant medications.

The number and percentage of study participants taking past, prior and concomitant medications will be summarized for the SS.

A by-study participant listing of all past, prior and concomitant medications will be provided on ES.

